8. RESEARCH QUESTION AND OBJECTIVES

The primary research question for this study is: What is the long-term safety in paediatric patients treated with somatrogon in real-world routine clinical practice?

Primary Objective:

Estimate the incidence rates of neoplasms, and diabetes mellitus type 2, the primary safety events of interest in paediatric patients treated with somatrogon, and paediatric patients treated with once daily somatropin, in the course of routine clinical care.

Secondary Objectives:

- a) Estimate the incidence rates of clinical endpoints related to immunogenicity, medication errors, the secondary safety events of interest, in paediatric patients treated with somatrogon, and paediatric patients treated with once daily somatropin, in the course of routine clinical care.
- b) Evaluate long-term efficacy by measuring IGF-1 levels, and height in paediatric patients treated with somatrogon, and paediatric patients treated with once daily somatropin, in the course of routine clinical care.
- c) Estimate the hazard ratios of neoplasms, and diabetes mellitus type 2, the primary safety events of interest between paediatric patients treated with somatrogon, and paediatric patients treated with once daily somatropin, in the course of routine clinical care.
- d) Estimate the hazard ratios of the clinical endpoints related to immunogenicity, the secondary safety events of interest, between paediatric patients treated with somatrogon, and paediatric patients treated with once daily somatropin, in the course of routine clinical care.

The safety events of interest noted above, are based on the current understanding of the important potential risks associated with somatrogon. However, other endpoints may be added as understanding of the safety profile of somatrogon evolves and feasibility of their assessment permits.

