9. RESEARCH METHODS

9.1. Study design

This is a population based cohort study using routinely collected electronic healthcare data in France, Spain, Sweden, and the UK, during a study period of February 2022 to February 2032. Table 1 summarizes these data sources and their capabilities of addressing research objectives. The study population will be comprised of paediatric patients (ie, patients from 3 years to below the age of 18) who initiate once weekly somatrogon following registration of the product in the EU and UK, and an internal comparator population of paediatric patients who initiate treatment with daily somatropin accrued during the same time period as the somatrogon treated patients.

Table 1. Summary of study objectives and country-specific databases that have data to address them.

	Système National des Donnees de Sante (SNDS)	Longitudinal Patient Database (LPD) in Spain	Sweden Growth Hormone Registry and national health and demographic registers	The Health Improvement Network (THIN)
Primary objective	yes	yes	yes	yes
Secondary objective 2a	yes*	yes	yes	yes***,†
Secondary objective 2b	no	no	yes	no
Secondary objective 2c	yes	yes	yes	yes
Secondary objective 2d	yes**	yes	yes	yes [†]

^{*}not for medication errors as weight is not collected in this database.

† not for all immunogenicity clinical endpoints.

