9.3. Variables

Operational definitions of the following variables will be described in the statistical analysis plan (SAP).

Exposure:

- First filled Somatrogon prescription/dispensing following registration of the product in EU and UK.
- For the internal comparator, first filled somatropin prescription during the same study period as somatrogon patients.

As noted above, operational definitions of exposure will be specified in the SAP (eg, if feasible and subject to sample size, by: somatrogon use, those who switch between somatrogon and somatropin, or somatropin use).

Outcomes

The following are the safety events of interest:

Primary-

- neoplasms
- diabetes mellitus type 2

Secondary-

• immunogenicity

Where feasible, to evaluate immunogenicity within the respective databases, the following clinical endpoints related to immunogenicity will be captured:

- o Bronchospasm
- Allergic conjunctivitis
- o Allergic dermatitis
- Atopic dermatitis
- Eyelid oedema
- Henoch-Schonlein purpura
- Hypersensitivity
- o Rash
- o Allergic rhinitis
- Swelling face
- Swelling of eyelid
- Urticaria
- Medication errors

Where feasible, to evaluate medication errors for somatrogon within the respective databases, utilizing prescription information and weight

measurements, the following endpoints related to medication errors will be captured:

- Underdosing defined as a:
 - 50% decrease in dose for a single administration (or, dispensing that is <0.33 mg/kg body weight)
 - o Missing a dose within the course of 2 weeks
- Overdosing defined as:
 - o 50% increase in dose for a single administration (or, dispensing that is >0.99 mg/kg body weight)
 - O An extra dose administration within 4 days of the last dose

(The recommended dose for somatrogon is 0.66 mg per kilogram of body weight via a single weekly injection, adjusted by the doctor if necessary.)

For somatropin, the recommended dose in mg per kilogram of body weight via a daily injection, will be manufacturer dependent. Analogous to somatrogon, underdosing and overdosing will be defined as a 50% decrease and increase in dose for a single administration, respectively.

• Long-term efficacy

Where feasible, to evaluate long-term efficacy within the Swedish Growth Hormone Registry database, the following endpoints related to long-term efficacy will be captured:

- o IGF-1 levels
- Height (height velocity (HV), height standard deviation score (SDS), change in height SDS, and final height).

Covariates:

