9.7. Data analysis

The primary analysis will be descriptive and all eligible patients during the study period will be included, with no upper limit on the sample size. Due to database heterogeneity, analyses will be conducted separately by data source and data will not be pooled.

Baseline demographic and clinical characteristics for each treatment group will be described. For all the safety events of interest and efficacy measurements of interest, descriptive statistics, counts and proportions, crude incidence rates (ie, number of events per person years) and age/sex standardized incidence rates with associated two-sided 95% confidence intervals will be calculated as appropriate.

The summary of event rates will be based on survival analysis of time to first event based on an index date defined for each treatment group with appropriate censoring rules applied for those who do not experience an event by end of follow-up period including those who die, those who are lost to follow-up (eg, via migration out of the country as documented in the data source), or end of study period. Rates will be expressed as events/1,000 person-years of follow-up.

The primary objective of the study is active surveillance (to estimate the incidence rates of neoplasms, and diabetes mellitus type 2, the primary safety events of interest in paediatric patients treated with somatrogon, and paediatric patients treated with once daily somatropin, in the course of routine clinical care). Conducting quantitative, confounding-controlled comparative analyses will depend on having a sufficient sample size. The feasibility of more formal comparative analyses to evaluate safety events of interest that adequately adjust for potential confounders will be assessed in the interim reports, and at study end will be based on statistical power as described below. Since the size of the once daily somatropin-treated comparator group is expected to be a magnitude larger than the somatrogon-treated group,

statistical power will be limited by the uptake of somatrogon (which is difficult to estimate a priori).

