As described in Section 9.5 (Study Size), the comparative analyses by data source will only be performed at the time of the final report if the number of patients in the somatrogon treated group would allow for an HR of 3.00 or higher to be detected with 80% power at the 5% significance level, assuming 0% annual switching between somatrogon and once daily somatropin-treated groups. Specifically, comparative analyses by data source for:

- neoplasms will only be performed at time of the final report if there are $\ge 1,305$ patients in the somatrogon-treated group
- Diabetes mellitus type 2 will only be performed at time of the final report if there are ≥2,344 patients in the somatrogon-treated group.

If comparative analyses can be performed, incidence rates of the primary safety events of interest will be compared between somatrogon-treated patients and the comparator group of daily somatropin-treated patients using multivariable Cox regressions adjusting for potential confounders. The adjusted hazard ratio from the Cox model will be presented along with a 95% confidence interval.

Given the low number of patients anticipated to have IGF-1 laboratory results, height, and weight measurements, and the high potential for missing values/measurements for some clinic visits, no comparative analysis for IGF-1, height, and medication errors will be conducted.

Detailed methodology for summary and statistical analyses of data collected in this study will be documented in a SAP, which will be dated, filed and maintained by the sponsor. The SAP may modify the plans outlined in the protocol; any major modifications of primary endpoint definitions or their analyses would be reflected in a protocol amendment.

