- The secondary objective of 'evaluating long-term efficacy by measuring IGF-1 levels, and height in paediatric patients treated with somatrogon, and paediatric patients treated with once daily somatropin, in the course of routine clinical care, will only be evaluated in Sweden (using data from the National Swedish Growth Hormone Registry), and if feasible, in a portion of patients in the UK THIN database when IGF-1 laboratory results, pubertal staging, height, and weight measurements are available. Similarly, the secondary objective to 'estimate the incidence rates of medication errors', will be evaluated in Sweden only, and if feasible, in UK THIN and Spain's LPD, but not SNDS. Laboratory data, height, and weight measurements are not available in the French SNDS claims database. Laboratory data values (eg, IGF-1) are not available in the Spanish LPD database.
- The French SNDS, Spain LPD, UK THIN, and Swedish databases and registry, respectively, do not capture administration of medications. SNDS and THIN provide reimbursed prescription data. Spanish IQVIA LPD databases do not capture the dispensation of the medication, only the prescription (dose and frequency). Whereas the Swedish registry provides dispensation data. While dispensation is a good proxy for administration there is still the possibility that a medication was dispensed but not taken. [Velentgas 2013].
- Exact injected dosing will be unknown. In Sweden, SNDS, Spanish LPD, and THIN, dosing will be based on packaging and frequency of reimbursed prescriptions. For Sweden's PDR, exact dosage will not be available but dose will be based on packaging, frequency of prescriptions, amount and strength dispensed.
- For SNDS only, clinical outcomes such as immunogenicity are only captured in hospitalisation data since outpatient diagnosis data are not available in this data source (to note, some diagnoses could be available in the outpatient database as reasons for registration in the long-term disease database; such chronic conditions are identified with ICD-10 codes).

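### Medication errors: missed and extra doses count as under/overdosing for somatrogon but not for somatropin, so the two descriptive rates have different definitions

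*Protocol*

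**What the plan says.** Secondary objective (a) in Section 8 of the protocol is to "Estimate the incidence rates of clinical endpoints related to immunogenicity, medication errors, the secondary safety events of interest, in paediatric patients treated with somatrogon", and it continues to the once-daily somatropin group. Section 9.7 sets out the output: "For all the safety events of interest and efficacy measurements of interest, descriptive statistics, counts and proportions, crude incidence rates", plus age- and sex-standardised rates, summarised as time to first event.

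Section 9.3 defines the events. For somatrogon, underdosing is a dose 50% too low (or a dispensing below 0.33 mg/kg) or "Missing a dose within the course of 2 weeks". Overdosing is a dose 50% too high (or a dispensing above 0.99 mg/kg) or "An extra dose administration within 4 days of the last dose". For somatropin, after noting that the recommended dose depends on the manufacturer, the whole definition is: "Analogous to somatrogon, underdosing and overdosing will be defined as a 50% decrease and increase in dose for a single administration, respectively".

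Two statements limit the reach of this endpoint. A footnote to Table 1 in Section 9.1 excludes the French source: "not for medication errors as weight is not collected in this database". Section 9.7 adds that "no comparative analysis for IGF-1, height, and medication errors will be conducted".

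**The concern.** The somatropin definition is presented as the analogue of the somatrogon one but carries over only half of it. The dose-size items match; the two schedule items have no somatropin counterpart in Section 9.3 or elsewhere. The report would then show two rates under one label with different definitions of an event.

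A reader who sees a higher medication-error rate for somatrogon could not tell whether dosing errors are more frequent with the weekly product or whether more kinds of error were counted. The omission also matters for the comparator. Section 7 argues that the burden of daily injections may lower compliance, yet a missed daily dose cannot count as somatropin underdosing. Section 9.9 lists several limits on measuring medication errors, but not this one.

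**Working it through.** **1. The plan's own thresholds.** Section 9.3 gives a recommended weekly somatrogon dose of 0.66 mg/kg. Minus 50%: 0.66 × 0.5 = 0.33 mg/kg. Plus 50%: 0.66 × 1.5 = 0.99 mg/kg. Both stated cut-offs reproduce, so the dose-size items are sound.

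**2. Items by product (Section 9.3).**

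| Item | Somatrogon | Somatropin |
|---|---|---|
| Dose 50% too low | yes | yes |
| Missed dose (2-week window) | yes | not stated |
| Dose 50% too high | yes | yes |
| Extra dose (within 4 days) | yes | not stated |
| Total | 2 + 2 = 4 | 1 + 1 = 2 |

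**3. Direction.** Section 9.7 bases rates on time to first event. Adding a qualifying item can turn a patient without an event into one with an event, or bring the first event forward. It can never remove an event or lengthen the time at risk. Events divided by person-years therefore cannot fall, so the two extra items either leave the somatrogon rate unchanged or raise it. They have no effect on the somatropin rate.

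**4. Data sources affected.** Four sources minus SNDS leaves at most three. Section 9.9 narrows this to Sweden, with THIN and LPD only if feasible.

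**5. Can the schedule items be observed?** Section 9.9 says the sources "do not capture administration of medications", that errors of timing will not be captured, and that accuracy for a single dose or week is limited. The only direct missed-dose signal described is the Swedish growth hormone registry, where providers report missing doses every 6 months and medication errors are held as a 3- to 6-month aggregate. In two-week windows that is 13 weeks / 2 = 6.5 up to 26 weeks / 2 = 13. The aggregate alone therefore cannot show which two-week window contained the missed dose. No source is described as giving a direct extra-dose signal.

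**6. Size.** The protocol gives no missed-dose, extra-dose or dose-size error rate, so no ratio between the two rates can be computed. The excess starts at zero, if no schedule error is recorded, and has no upper bound that the protocol supports.

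**The case against.** The strongest reply has four parts.

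- **Definitions are deferred.** Section 9.3 leaves operational definitions to the SAP, which is not available here. The somatropin sentence does not say that dose size is the only criterion, and nothing states explicitly that the items are summed. This carries limited weight. The protocol lists both items under a single definition of underdosing and does the same for overdosing. It also states a somatropin definition rather than leaving one open.
- **The windows are made for weekly dosing.** A second somatropin injection within 4 days is correct use, so the somatrogon items cannot be transferred unchanged. That is true. It is a reason to show schedule errors separately or to adapt the measure, not to put them in one group's rate only.
- **Schedule errors will hardly be seen.** This stands as a limit on importance, since the practical difference may be negligible. It does not make the definitions equal, and the Swedish registry does hold one missed-dose signal, which Section 9.9 does not restrict to one product.
- **No comparison is planned.** This also stands: no hazard ratio, test or sample size depends on the endpoint. Objective (a) still calls for both rates, and readers will set them side by side.

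**Conclusion.** The concern holds and is of minor importance. As written, Section 9.3 gives four qualifying items for somatrogon and two for somatropin, and Section 9.9 does not disclose the difference. Any bias in reading the two rates together runs toward a higher somatrogon rate; its size is unknown and may be nil. The conclusion assumes that under/overdosing is analysed as defined in Section 9.3, without a schedule criterion for somatropin being added later. It touches a secondary, descriptive endpoint assessed where feasible in at most three of four sources. The primary objective and all planned hazard ratios are unaffected, and the shared dose-size part could be compared if it were shown alone.

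**What to change.** In Sections 9.3 and 9.7, and correspondingly in the SAP:

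- Report the 50% dose-size component as its own under/overdosing rate, defined in the same way for both products.
- Report missed-dose and extra-dose events in separate rows labelled somatrogon-only, and do not add them to that rate.
- Where the data allow, use one missed-dose measure built identically for both products. An example is provider-reported missing doses per 6-month report in the Swedish registry, in place of the two-week window.

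The cost is protocol and SAP wording plus a few table rows, with no new data. The one drawback is that the headline somatrogon rate would no longer include schedule errors, which would be read from their own rows.

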9.4. Data sources

This study plans to utilize administrative healthcare databases in France, electronic secondary data collected in the Spain LPD database, the national population-based electronic healthcare registers in Sweden, and electronic primary healthcare records database in the UK. These secondary data sources are selected based on the availability of the expected required data elements and projected number of patients with somatrogon exposure post-approval within the data source country. The inclusion of their data in all reports will reflect data availability at the time of data base lock for each report. The proposed data sources are briefly described below:

- France-The French administrative health care claims database ('Système National des Données de Santé', SNDS) covers approximately 99% of the total 67 million population. In addition to demographic characteristics, SNDS contains outpatient data including drugs dispensation with number of units, laboratory tests performed (tests results are not captured), and registration status in the long-term disease database for chronic conditions identified with ICD-10 codes. In SNDS, somatrogon (and somatropin) will be mainly self-administered by the patient in the outpatient sector (including a first administration supervised by a physician). In the case where treatment is administered and invoiced during a hospitalization, data will be available only if the treatment is registered in the 'list en sus' or 'retrocession list'. The outpatient data are linked to hospitalisation data (national hospital discharge database, PMSI) through a unique personal identification number (Scailteux and Droitcourt, 2019). The PMSI captures information relating to inpatient or ambulatory care admissions to a public or private hospital in France, including discharge diagnoses, procedures and drugs administered during hospitalization and invoiced in addition to the diagnosis-related group (DRG). All diagnoses are coded according to ICD-10. Height and weight measurements are not available in this claims database. The contents of SNDS include but are not limited to:
 - Sociodemographics: age (through date of birth (MMYY)), sex, lowest income level (based upon whether patient is a recipient of basic universal health coverage), and deprivation index.
 - Hospital data: date of admission, ward type, admission following ER visit (yes/no), date of discharge, discharge diagnoses (1 principal, 1 related and up to 50 associated), DRG, procedures, drugs invoiced in addition to the DRG, external consultation at hospital, and costs.

- Outpatient prescription data: number of prescriptions reimbursed, prescriber's specialty, and costs.
- o Pharmaceutical information:
 - Outpatient (community pharmacy): brand, generic name, Anatomical Therapeutic Chemical (ATC) code, CIP code ('Code Identifiant de Présentation', for each specific packaging), size, strength.
 - Inpatient (hospital: list 'en sus', retrocession list): brand, generic name, ATC code, UCD code ('Unité Commune de Dispensation', for the smallest unit of dispensation [eg, pill, vial]), dosage form and strength, amount administered.

Lag in data availability for SNDS varies from 1 month (outpatient data) to 12 months (hospital data).

• Spain-The LPD database contains anonymized electronic data collected from approximately 3,000 office-based primary and secondary physicians, representing about one million patients (covering approximately 3% of the national population). The patient population is representative of the Spanish population according to geographic coverage, and age and gender distribution, as provided by the Instituto Nacional de Estadística (INE). Healthcare contacts done outside of the national health system are not captured (private sector).

The electronic medical records (EMR) collect medical information from the practice management software used by the physician during patients' office visits for recording their daily patient interactions in EMRs. The panel of contributing physicians is maintained as a representative sample of the primary care and specialist physician population in Spain. Panel physicians volunteer to make available anonymized, patient-level information from their practices for clinical research purposes.

The patient identifier is unique through all general practitioner and specialist practices. Data are captured directly from patients' EMRs, with no intervention being made to collect or complete the data. The LPD is therefore, secondary data collected in a non-interventional way, reflecting routine clinical practice. In-hospital treatment administration, including for somatrogon (or somatropin), is not available in the LPD database, only prescription at discharge is collected in these situations.

The unique patient identifier is used across all general and specialist visits, enabling longitudinal follow-up of patients in the Spanish LPD. Data available in the LPD include:

- o Demographic characteristics: age and gender only
- Outpatient data: The LPD provide systematic ongoing information from primary and secondary physician office-based visits on patients' consultations, diagnoses and treatments. In LPD, clinical outcomes are only captured in outpatient data. These diagnoses are directly recorded as International Classification of Diseases, Ninth Revision (ICD-9) codes.
- Outpatient prescription data: for prescribed and reimbursed medications there are prescription dates, ATC class codes, substance name, route of administration, strength, daily dose, and duration.
- Pharmaceutical information:
 - Outpatient (pharmacy): pharmacy dispensation is not available.
 - o Inpatient: Prescribed treatments at discharge, but not in-hospital administration, is collected.

Data are transmitted online on a monthly basis, and the lag in outpatient data availability for LPD is 1 month.

Sweden-The Swedish register system is a large, relatively complete source of population-based data, including data on the entire Swedish population (10.2 million in 2022). Based on each Swedish resident's unique personal identification number, issued to all Swedish residents alive in 1947 or born/immigrated thereafter, linkage of data from different registers is possible.[Ludvigsson et al 2009] The registers are maintained by governmental bodies (eg, the National Board of Health and Welfare, Statistics Sweden), who may perform data linkages and provide pseudonymized data for research purposes. In Sweden, somatrogon (and somatropin) will be available in the Prescribed Drug Register (PDR), as it will be exclusively introduced in the outpatient setting; if given during hospitalization it will not be in the PDR or National Patient Registry (NPR). The relevant databases that will be used in this study include the NPR, the PDR, the Cancer Register, [Barlow et al 2009] and the Cause of Death Register (CDR; Brooke et al 2017), and the demographic databases at Statistics Sweden. The National Swedish Growth Hormone can also be linked to the National Register data. Data on comorbidities and

hospitalization will be extracted from the Patient Register and the Cancer Registry. The relevant contents of registers include but are not limited to:

- Demographics: age, sex, place of residence, place of birth, citizenship, immigrant status, immigration date, race/ethnicity.
- Diagnoses made in in- and out-patient care, recorded by ICD codes, as well related admission and discharge dates. Incident cancer diagnosis is morphologically confirmed.
- Ambulatory prescription and dispensations: date, prescriber profession, brand name, formulation, package, DDD, dispensed amount, and expenditures. All drugs are classified according to the ATC classification system. [Wettermark et al 2007]
- O Growth data: Ethiology for GH treatment, co-morbidity and other hormone treatments, birth length and weight as well as gestational age, years on and start of growth hormone treatment, parental height, growth rate during first treatment year, weight and height at start and at puberty onset, age and final height, IGF-1 and GH maximum from 24-hr growth hormone profiling. [Emilsson et al 2015 for a general overview of treatment registries]

The lag time in diagnosis/prescription fill to the incorporation of data into the national registers is between 1 month and 1 year depending on the register. There is a 15-month lag between clinical data being entered into the system and the data being available for analysis (eg, the Cancer Registry has a delay of 15 months). The implication of this is that complete data for 2022 is available in the registers at the end of 2023. Additionally, there is typically a waiting time of 10-12 months between the time of data order submission and delivery of the data by the register holders.

• UK- The Health Improvement Network (THIN) database contains longitudinal, non-identified primary care EMR for approximately 4% of the UK population. This anonymised data collection, which goes back to 1994, is nationally representative of the UK population. This translates to more than 20 million historic patients and 2.3 million active patients. Preparations are underway to add an additional 1 million active patients into the panel over the coming year. Data collected from electronic general practitioners (GP) records include, but are not limited to: symptoms, diagnoses, and referrals (coded using the hierarchical Read code system), drug prescriptions (using ATC codes), lifestyle choices (eg, smoking and alcohol habits), biological measures (height and weight), laboratory tests (and results), and communication from secondary care providers in the form of digitalised letters (ie, free text). Treatment is administered in a "shared care" setting with primary care physicians (GPs) and secondary care providers sharing the patient. Communications between primary

and secondary care is in the form of letters. During this time the GP may read and code the letter into patient records (eg, patient height). Alternatively, the full letter might be appended to administrative read codes (eg, "letter received" corresponds to the read code 9N3D.00). Self-administration of somatrogon/somatropin are not captured in outpatient data (including first administration that is supervised by a physician). If somatrogon/somatropin are initiated while in secondary care (ie, hospitals, based on discharge summaries) and then continued in a primary care setting (ie, is a repeat medication), it will be captured in THIN. Feasibility assessments of this GP database indicate that at least one height measurement is available for approximately 40% of somatropin treated pediatric patients (<18 years at first prescription) and weight measurements for 48% of somatropin treated pediatric patients in this database. Laboratory results, specifically IGF-1, were available for 4% of approximately 2,300 patients (<18 years, with GHD) unique patients as of December 2020. Although two read codes were used (plasma IGF-1 level and serum insulin-like growth factor 1 level), these are poorly recorded in THIN's structured data. The contents of THIN include but are not limited to:

- Sociodemographic characteristics: age, sex, and ethnicity (ethnicity data is opt-in and is less well complete)
- o Hospital data: THIN is a primary care database. However, as described above, for patients who are managed in a hospital (ie, secondary care), the specialist relays patient information back to the GP via a letter. In this manner, data on outpatient and hospitalization visits and procedures are captured. The letter conveys a description of what events occurred. The letter can include but is not limited to diagnosis, signs/symptoms, drugs prescribed, biological measures such as height and weight, labs tests and lab results. It is also possible that the health care provider reads the letter and codes the information into the patient's record. Referrals to secondary settings and discharge letters back from secondary care to primary care setting are captured in the database and may be coded into the patient health record from the discharge letters or recorded as free text.
- Patient prescription data: prescribed products, the frequency and timing of prescriptions are captured. Repeat prescriptions are also recorded (date and quantity).

There is a 1-month lag between clinical data being entered into the system and the data being available for analysis.

